## 1.0 OBJECTIVES

# 1.1 Primary Objective

 To establish the safety of radiotherapy in the treatment of advanced hidradenitis suppurativa

# 1.2 Secondary Objectives

- To examine the efficacy of radiotherapy in improving quality of life for patients with advanced hidradenitis suppurativa
- To explore histologic changes following radiotherapy for advanced hidradenitis suppurativa
- To explore changes in ultrasound findings following radiotherapy for advanced hidradenitis suppurativa
- To determine possible changes in assessment of cutaneous discharge from HS lesions

## 2.0 BACKGROUND

# 2.1 Hidradenitis Suppurativa

Hidradenitits Suppurative (HS) is a chronic inflammatory skin disease characterized by recurrent, painful abscesses, sinus tracts, and scarring. The majority of HS lesions are found in apocrine bearing skin, which includes the axilla, groin, and inframammary regions. The etiology of HS is still unclear, but it is hypothesized that the lesions develop due to follicular occlusion where the aprocine gland meets the hair follicle. This follicular blockage leads to cyst formation. The colonization of the cyst by skin flora leads to an exuberant immune reaction to cyst contents that results in painful inflammation and abscess formation. The abscesses may heal over the following 1-2 weeks, leaving a scar. Even with treatment, inflammation can continue and lead to the formation of skin tracts that burrow in the dermis. Over time, the HS inflammation persists, and painful suppurating and connecting dermal tracts are found in the whole region, such as the axilla and groin. The impact of HS on quality of life can be devastating. Patients often report extreme embarrassment from the disfiguring lesions and their associated foul, odiferous discharge.

# 2.2 Current Treatment Options

There are only a few options for effective treatment of HS, and no definitive cure exists. Treatment depends on severity and clinical staging. The mainstay of treatment of mild disease involves antibacterial washes and topical antibiotics, and acute flares may be managed by intralesional corticosteroids and/or minor surgical procedures. Oral therapies include 3-6 months of broadspectrum antibiotics, oral anti-androgens may be helpful in women, and systemic retinoids (isotretinoin or acitretin) may be beneficial in a subset of patients. Laser hair removal with 1064nm Nd:Yag laser has shown promise, but many patients

cannot afford this treatment. The only FDA approved treatment for HS is adalimumab (Humira), an antibody against tumor necrosis factor  $\alpha$  (TNF- $\alpha$ )[1].

Patients who fail medical management or who are ineligible for TNF- $\alpha$  inhibitors are left with few options for salvage treatment. In this situation, patients will often resort to extensive surgical resection of the affected area with or without graft placement. Unfortunately, the recurrence rate of HS lesions in this area is high, with recurrence rates up to 50% of patients who have surgery. The use of a more "conservative" surgical approach, such as the CO2 laser to excise all apocrine bearing tissue, has shown potential for improved surgical results, but it's not widely available. In addition, recurrence of HS lesions still occurs in a number of patients who have undergone this laser procedure

As reviewed in above case report, a center in Germany treated 231 HS patients over 20 years who failed other treatment options. These patients received multiple fraction schedules with multiple fraction sizes (0.5 Gy - 1.5 Gy per fraction up to a total dose of 3.0 Gy to 8.0 Gy in one series). Chronic

recurrences were treated with 2 or more series with a total dose of greater than 10.0 Gy. No acute side effects were observed in this study. Complete symptomatic relief was documented in 38% (89/231) patients by the end of therapy and 40% (92 / 231) of patients reported an overall improvement in symptomatology. Only two patients had no response.

## 3.0 PATIENT ELIGIBILITY

Each of the criteria in the checklist that follows must be met in order for a patient to be considered eligible for this study.

#### 3.1 Inclusion Criteria

- The subject must be diagnosed with HS at Montefiore HS Treatment Center, with Hurley Stage 2-3 (Recurrent abscesses or boils with diffuse or broad involvement, multiple interconnected sinus tracts in the whole area) [5]. See Appendix A for photos.
- Subject must have failed maximal medical therapy for HS or be ineligible for "standard" medical therapy or surgery
- Age > 20 years old
- Women of childbearing potential must:
  - Have a negative serum or urine pregnancy test within 72 hours prior to the start of study therapy
  - Agree to utilize an adequate method of contraception throughout treatment and for at least 4 weeks after study therapy is completed. Adequate methods of contraception include hormonal methods (i.e. birth control pills, patches, injections, vaginal ring, or implants), barrier methods (i.e. condom or diaphragm), intrauterine device, or abstinence.
  - Be advised of the importance of avoiding pregnancy during trial participation and the potential risks of an unintentional pregnancy
- All patients must sign study specific informed consent prior to study entry.

## 4.0 STUDY DESIGN

# 4.1 General Design

• This phase I clinical trial will use a Simon two-stage design. In the first stage, 6 patients will be enrolled, if the patients in the study do not meet the termination criteria then the study will extend to a second stage and we will enroll a maximum of 20 patients. Patients will be treated with skindirected radiotherapy, using a total prescription dose of 7.5 Gy in five fractions of 1.5 Gy over one week. Neither patient nor insurance will be billed for the radiotherapy procedures. If any subject experiences Grade > 3 toxicities, the study will be stopped and the IRB will be informed immediately so the study can be reevaluated.

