#### Interim Analysis.

Once the first 6 patients are recruited, the study recruitment will be temporarily suspended and the patients will be followed for 3 months to monitor any toxicity issues. At the end of 3 months follow-up of the 6 patients, the results will be sent to the DSMB for further evaluation. The trial will be terminated if grade 3 or more toxicity is observed in more than 2 patients or at least one showing grade 4 level toxicity. Otherwise, upon approval from the DSMB, the second phase of recruiting will be initiated.

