#### 5.0 STATISTICAL CONSIDERATIONS

A maximum of 20 patients will be enrolled into the study. The accrual rate is expected to be 1-2 patients per month based on the volume of patients with stage 2-3 HS treated within the Montefiore Hidradenitis Suppurativa Treatment Center. An early stopping rule for safety will be implemented as follows based on Simon's optimal two-stage design. After the first 6 patients have been enrolled, accrual will be temporarily suspended while these patients are monitored for occurrence of treatment-related grade ≥ 3 toxicity for 3 months. At the end of 3

months, results will be sent to the DSMB for further evaluation. The trial will be terminated early if more than 1 patient experiences grade  $\geq$  3 treatment related toxicity or any patient experiences grade 4 toxicity. Otherwise, upon approval from the DSMB, the second phase of recruiting will be initiated. If 1 or fewer grade  $\geq$  3 toxicities and 0 grade 4 toxicities are observed, the trial will continue until a total of 20 patients have been evaluated. At the end of the trial, the treatment will be considered safe and worthy of further study if no more than 3 patients experience grade  $\geq$  3 treatment related toxicity and none experience grade 4 treatment related toxicity.

The target Grade  $\geq$  3 toxicity rates is no more than 10%, and a toxicity rate greater than 30% is considered clinically unacceptable. The design specified above has the following operating characteristics. The probability of accepting the treatment for further study if the toxicity rate is unacceptably high (> 30%) is at most 10%. In contrast, there is an 80% probability of accepting the treatment for further study if the toxicity rate is less than 10%. In addition, if 0 out of 20 patients experience Grade 4 toxicity at the end of the study, we will be able to conclude with 95% confidence that the true Grade 4 toxicity rate is not greater than 17%.

The proportion of patients who have treatment-related toxicity will be computed, along with exact 95% confidence intervals. Since the study is a phase I trial, we will NOT do any hypothesis testing or models, The study will present the descriptive summary statistics for each outcomes. Biomarker levels measured at different time points and other continuous variables will be summarized by computing means, medians, standard deviations and ranges.

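### Sections 4.1 and 5.0 attach different consequences to a Grade 4 toxicity and do not say how their rules fit together

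*Combined protocol and SAP*

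**What the plan says.** Four places bear on a Grade 4 event.

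- **Section 4.1, General Design.** The trigger is any subject with a toxicity above Grade 3. The action is that "the study will be stopped and the IRB will be informed immediately so the study can be reevaluated". No look, time window or attribution to treatment is attached.
- **Interim Analysis text under Section 4.1.** The timing is: "At the end of 3 months follow-up of the 6 patients, the results will be sent to the DSMB for further evaluation". Termination follows if Grade 3 or worse is "observed in more than 2 patients", "or at least one showing grade 4 level toxicity".
- **Section 5.0.** At the same look: "The trial will be terminated early if more than 1 patient experiences grade" 3 or worse related to treatment, or if "any patient experiences grade 4 toxicity". If neither condition is met, and subject to DSMB approval, "the trial will continue until a total of 20 patients have been evaluated". At the end, the treatment is judged acceptable only if at most 3 patients had treatment-related Grade 3 or worse and none had treatment-related Grade 4.
- **Section 8.0.** The monitoring committee reviews events of Grade 3 or higher, meets quarterly or more often, and may close accrual if risk is excessive.

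No section refers to another on this point or says which governs.

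**The concern.** Safety is the primary objective (Section 1.1) and the primary endpoint (Section 4.3), so the response to a Grade 4 event is central to how this trial is run. A stop for re-evaluation and a mandatory termination are different outcomes, and the texts name different bodies: the IRB in Section 4.1, the DSMB in the Interim Analysis text and Section 5.0. An investigator with a Grade 4 event in stage 1 cannot tell from the protocol whether the trial may resume. In stage 2, a reader of the statistical section alone would find no instruction to halt. If the trial does resume after a treatment-related Grade 4 event, the final acceptance criterion has already failed, and nothing says what treating further patients could then show.

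**Working it through.** **1. The plan's own figures.** Inputs from Section 5.0: 6 patients then 20 in total; go on if at most 1 of 6 has Grade ≥ 3; accept if at most 3 of 20; toxicity rates p of 10% and 30%. Ignoring the Grade 4 clauses,

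P(accept) = P(X₁=0)·P(X₂≤3) + P(X₁=1)·P(X₂≤2), with X₁ ~ Bin(6, p) and X₂ ~ Bin(14, p).

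- p = 10%: 0.5314 × 0.9559 + 0.3543 × 0.8416 = 0.806 (stated: 80%).
- p = 30%: 0.1176 × 0.3552 + 0.3025 × 0.1608 = 0.090 (stated: at most 10%).
- Upper bound for 0 of 20 with Grade 4: 1 − 0.025^(1/20) = 16.8% (stated: 17%).

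The figures reproduce, but only with the Grade 4 clauses left out. Adding a zero-Grade-4 requirement, and assuming that all events are treatment-related and that 10% to 50% of Grade ≥ 3 events are Grade 4, lowers acceptance at p = 10% from 0.806 to between 0.688 and 0.341. The stated operating characteristics therefore do not help to decide how the Grade 4 rules were meant to work.

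**2. The texts side by side.**

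| Event | Section 4.1 | Interim Analysis text | Section 5.0 |
|---|---|---|---|
| Grade 4 in patients 1–6 | Stop; IRB informed at once; re-evaluate | Terminate at the look | Terminate at the look |
| Grade 4 in patients 7–20 | Stop; IRB informed at once; re-evaluate | Silent | No stop stated; a treatment-related event fails the final criterion |
| Attribution | Not limited | Not limited | Grade 4 not limited at the look; treatment-related at the end |
| Grade 5 | Covered by > 3 | Not literally in the Grade 4 clause | Not literally in the Grade 4 clauses |

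*Stage 1.* Suppose patient 2 has a Grade 4 event, the study stops under Section 4.1, and re-evaluation allows it to resume. At the 6-patient look the other two texts require termination because that event has occurred. The restart leads to a look whose result is already fixed. Read literally, this holds even if the event was found to be unrelated.

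*Stage 2.* Suppose patient 8 has a Grade 4 event. Section 4.1 stops the study. If it resumes, the final criterion has failed if the event was treatment-related, and can still be met if it was not.

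**3. Upper limits on further enrolment**, if the Section 4.1 halt is not followed and the committee does not close accrual.

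- Stage 1, event in patient 1: 6 − 1 = 5 further patients. At the stated 1–2 per month, 5/2 to 5/1 = 2.5 to 5 months, plus 3 months of follow-up before the look.
- Stage 2, event in patient 7: 20 − 7 = 13 further patients.
- Section 4.1 followed: 0 until re-evaluation.

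**4. How often the stage 2 question would arise.** The documents give no Grade 4 rate, so g is an assumption. The chance of no Grade 4 in the first 6 and at least one in the next 14 is (1−g)⁶ × [1 − (1−g)¹⁴]. The mean number of patients after the first such event is Σ(14−i)·g(1−g)^(i−1) / [1 − (1−g)¹⁴], for i = 1 to 14.

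| Assumed g | First Grade 4 falls in stage 2 | Mean patients still to come |
|---|---|---|
| 1% | 12.4% | 6.7 |
| 2% | 21.8% | 6.8 |
| 5% | 37.7% | 7.3 |
| 10% | 41.0% | 8.2 |

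**The case against.** A reader might infer a direct clash on timing: that Section 4.1 stops at any moment while the other texts act only at the two looks, so that Section 5.0 tells the team to keep enrolling after a Grade 4 event. The documents do not support that.

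- An event-driven halt and scheduled looks can operate together. Neither the Interim Analysis text nor Section 5.0 excludes an earlier stop, and a restriction to the looks would be an inference from silence.
- The sentence about continuing to 20 patients is conditional on no Grade 4 and at most one Grade ≥ 3 event, most naturally at the first look. It does not instruct accrual after a stage 2 event.
- The end-of-trial clause is an acceptance criterion, not a competing stopping rule. It is limited to treatment-related events, so a Grade 4 event does not always defeat it.
- Section 8.0 gives the committee a route to close accrual outside the looks.
- The counts of 5 and 13 are ceilings. With 3 months of follow-up and 1–2 patients per month, some of those patients could already be enrolled when the event appears, whatever the rule.
- For a treatment-related Grade 4 event, the final accept/reject result is the same on every reading.

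All of this stands. It does not remove the difference in consequence: on a layered reading, Section 4.1 still leaves room to resume where the other two texts require termination. The committee's power in Section 8.0 is discretionary and does not settle which rule governs. The identical final verdict is of limited comfort, because a stopping rule exists to limit exposure before that verdict.

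**Conclusion.** The point holds as a conflict of consequence and a gap in stage 2, not as a conflict of timing. For a Grade 4 event in the first 6 patients, the plan both provides for re-evaluation with restart not excluded and requires termination at the look. For patients 7 to 20, the halt rests on one sentence in Section 4.1 that the statistical section does not repeat. The size is at most 5 further enrolments in stage 1 and 13 in stage 2, and those limits apply only if Section 4.1 is not followed and the committee does not act. The stage 2 probabilities rest on assumed Grade 4 rates of 1% to 10%. Because the event concerns the primary endpoint and the correction changes what the trial does after it, the texts should be reconciled.

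**What to change.** Reconcile Section 4.1, the Interim Analysis text and Section 5.0, with a reference to Section 8.0, and use the same wording in Sections 4.1 and 5.0. For each stage, state:

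- whether the Section 4.1 halt applies alongside the scheduled looks;
- whether the result is suspension pending review or termination;
- which body decides;
- whether the trigger is limited to treatment-related events, and whether it covers Grade 5.

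If restart is allowed, say that after a treatment-related Grade 4 event the Section 5.0 acceptance criterion cannot be met, and what further enrolment could then conclude. After an unrelated event the criterion can still be met, so the treatment-related limit must stay in that statement.

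The same paragraph should settle the Grade ≥ 3 threshold at the 6-patient look, which is more than 2 in the Interim Analysis text and more than 1 in Section 5.0. The stated operating characteristics match more than 1; more than 2 gives an acceptance probability of 0.106 at 30% toxicity, above the stated 10%.

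The cost is one amendment paragraph, with no added patients or data. Which rule applies is for the sponsor to choose.

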#### Interim Analysis.

Once the first 6 patients are recruited, the study recruitment will be temporarily suspended and the patients will be followed for 3 months to monitor any toxicity issues. At the end of 3 months follow-up of the 6 patients, the results will be sent to the DSMB for further evaluation. The trial will be terminated if grade 3 or more toxicity is observed in more than 2 patients or at least one showing grade 4 level toxicity. Otherwise, upon approval from the DSMB, the second phase of recruiting will be initiated.

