# 4.3 Study Endpoints

The primary endpoint of this study is safety, defined as the absence of any treatment-related Grade ≥3 adverse events during radiotherapy or within 3 months of radiotherapy completion, scored using CTCAE version 4.0.[6] Secondary study endpoints include:

# Optional

- Quality of Life
  - Improvement in NIH Patient-Reported Outcomes Measurement Information System (PROMIS) measures, including pain interference and physical functioning at 3 months (and optionally at 6 months and 12 months) after treatment[7, 8]
    - A one point change, either positive (improvement) or negative (decline), will be considered to be clinically meaningful[9]
- Inflammation as measured by ultrasound.
  - Noninvasive imaging, such as ultrasound (US), allows for an objective assessment of subclinical disease activity.
  - Anechoic area will be measured in the dermis before and after treatment, as well as other sonographic criteria of HS [10](See Appendix for Sonographic Scoring and Diagnosis of HS)
  - As there are no validated ultrasound criteria to measure clinical improvement, reduction in anechoic areas and sonographic criteria will be calculated. It is estimated that the treatment will induce a 50% reduction in the anechoic area.
  - Anechoic areas and other sonographic criteria will be correlated with PROMIS scores and Hurley Staging.
- Evaluation of cutaneous discharge
  - Swabs will be collected from discharge and sent for fluid count, which will include evaluation of infiltrating leukocytes from the discharge.
- Immunohistochemical Evaluation of HS Tissue Biopsies
  - Tissue biopsies will be collected before and after treatment. Tissue sections will be evaluated by H&E as well as immunohistochemistry for infiltrating leukocytes and other cells, such as T cells, B cells, plasma cells, dendritic cells, macrophages, and keratin. Image J will be used to quantify cells in a standard manner for comparison before and after treatment.

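### The stage 1 stopping boundary is more than 2 of 6 patients in Section 4.1 but more than 1 of 6 in Section 5.0; only the Section 5.0 rule is the stated Simon optimal design

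*Combined protocol and SAP*

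**What the plan says.** Section 4.1 (Interim Analysis) and Section 5.0 describe the same event: accrual pauses after 6 patients, they are followed for 3 months, and the results go to the DSMB.

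- **Section 4.1, Interim Analysis:** "The trial will be terminated if grade 3 or more toxicity is observed in more than 2 patients", or if at least one patient has grade 4 toxicity. If not, "Otherwise, upon approval from the DSMB, the second phase of recruiting will be initiated".
- **Section 5.0:** "The trial will be terminated early if more than 1 patient experiences grade" ≥3 treatment-related toxicity, or if any patient has grade 4 toxicity. The same limit is then restated from the other side: the trial goes on with 1 or fewer grade ≥3 toxicities and no grade 4.

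Section 5.0 introduces its rule with "An early stopping rule for safety will be implemented as follows based on Simon's optimal two-stage design". It sets a final limit of 3 of 20 patients with grade ≥3 treatment-related toxicity and none at grade 4. It takes 10% as the target rate and more than 30% as unacceptable. It claims at most a 10% chance of accepting an unacceptable treatment and an 80% chance of accepting an acceptable one. Section 4.1 attaches no operating characteristics to its boundary.

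**The concern.** The two boundaries disagree on one stage 1 result: exactly 2 of 6 patients with Grade 3 toxicity and none with Grade 4. Section 5.0 then stops the trial. Section 4.1 does not, and leaves stage 2 to DSMB approval. Nothing in the documents says which section prevails.

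This is the only scheduled interim analysis, and it is the gate to exposing up to 14 more patients (20 − 6) in a trial whose primary objective is safety. A team working from the paragraph headed Interim Analysis would apply the laxer rule, and the error rates in Section 5.0 would no longer describe the trial. If the conflict came to light only after 2 of 6 had been seen, the choice of boundary would be made with the data in hand.

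**Working it through.** **Inputs** (all from Section 5.0 unless noted): stage 1 size 6; maximum 20, so stage 2 size 14; final limit 3 of 20; toxicity rates p = 10% and 30%; claimed acceptance at most 10% at p = 30% and 80% at p = 10%. The highest stage 1 count that permits continuation, r, is 1 in Section 5.0 and 2 in Section 4.1.

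**Formulas, count rule alone** (no Grade 4 stop; the DSMB is assumed to approve stage 2 whenever the rule permits):

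- Early stop = 1 − Σ_{x≤r} C(6,x) pˣ(1−p)⁶⁻ˣ
- Expected N = 6 + 14 × (1 − early stop)
- Accept = Σ_{x≤r} P(X₁ = x) × P(X₂ ≤ 3 − x), with X₁ ~ Bin(6, p) and X₂ ~ Bin(14, p)

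**Step 1. Reproduce the plan's figures with r = 1.**

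- p = 30%: P(X₁ = 0) = 0.1176, P(X₁ = 1) = 0.3025; P(X₂ ≤ 3) = 0.3552, P(X₂ ≤ 2) = 0.1608. Accept = 0.1176 × 0.3552 + 0.3025 × 0.1608 = 0.0904.
- p = 10%: P(X₁ = 0) = 0.5314, P(X₁ = 1) = 0.3543; P(X₂ ≤ 3) = 0.9559, P(X₂ ≤ 2) = 0.8416. Accept = 0.5314 × 0.9559 + 0.3543 × 0.8416 = 0.8062.

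These match the claimed limits of 10% and 80%.

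**Step 2. Check the design label.** A search over designs up to N = 35 (false acceptance ≤ 10%, acceptance ≥ 80%, smallest expected N at 30% toxicity) returns 6 patients with ≤1, then 20 with ≤3, at expected N 11.88. The next best is 7 with ≤1, then 23 with ≤4, at 12.27. The first is the only qualifying design with 6 in stage 1 and 20 in total. So Section 5.0's boundary is the named optimal design, and a boundary of more than 2 of 6 is not.

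**Step 3. Put in the Section 4.1 boundary (r = 2), same final limit.** The extra term is P(X₁ = 2), which is 0.3241 at 30% toxicity and 0.0984 at 10%. This is also the probability that the two rules disagree.

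| Count rule | Stop if >1 of 6 | Stop if >2 of 6 |
|---|---|---|
| Early stop at 30% | 58.0% | 25.6% |
| Expected N at 30% | 11.9 | 16.4 |
| Accept at 30% | 9.0% | 10.6% |
| Accept at 10% | 80.6% | 86.4% |

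**Step 4. Add the any-Grade-4 stop.** The documents give no Grade 4 rate, so let s be an assumed share of grade ≥3 events that are Grade 4 or higher. Continuing then needs Grade 3 events only, so p is replaced by p(1−s) for each patient with toxicity, and 1−p is kept for each without.

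| Assumed s | Early stop at 30%, >1 | Early stop at 30%, >2 | Accept at 30%, >2 |
|---|---|---|---|
| 0 | 58.0% | 25.6% | 10.6% |
| 2% | 58.6% | 27.5% | 10.05% |
| 5% | 59.5% | 30.2% | 9.3% |
| 10% | 61.0% | 34.8% | 8.1% |
| 20% | 64.0% | 43.3% | 6.0% |

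The excess over 10% false acceptance disappears above s of about 2.2%. Early stopping under the Section 4.1 boundary is less than half that under Section 5.0 only up to s of about 4.4%. The difference between the two columns is 32.4 points at s = 0 and 20.7 points at s = 20%. It equals the probability that the rules give opposite instructions.

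**The case against.** The strongest objection is that neither section's full rule is the count rule. Both add a stop for any Grade 4 event, and with that stop Section 5.0's 80% no longer holds exactly: acceptance at 10% toxicity under the >1 boundary is 79.4% at s = 1% and 74.5% at s = 5%. For s between about 2.2% and 4.7%, the >2 boundary meets both stated limits while the >1 boundary misses 80%. At s = 3%, for example, >2 gives 9.8% and 82.2%, and >1 gives 8.4% and 76.9%. On this view the error rates alone do not show which number was meant.

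This stands as a limit on the error-rate argument: the 80% is a count-rule figure, and the 10.6% false acceptance is a small excess that depends on s. It does not change which number is wrong. Section 5.0 names the optimal design, states its stage 1 limit twice, and is matched by exactly one design with 6 and 20 patients.

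Safeguards are the second objection. Section 4.1 (General Design) has its own stop: "If any subject experiences Grade > 3 toxicities, the study will be stopped". The committee in Section 8.0 reviews events of grade 3 or higher and can close accrual. Stage 2 needs DSMB approval under either text, so 25.6% is a lower bound on stopping. All true, but two Grade 3 events do not trigger the Grade > 3 stop, Section 8.0 gives no count, and discretion to approve does not replace a mandatory stop.

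Third, toxicity may be rare: Section 10.0 rates dermatitis risk as very low, and Section 2.3 reports no acute side effects in a series of 231 patients. At assumed true rates of 5% and 2%, exactly 2 of 6 has probability 3.1% and 0.6%. That lowers the chance that the conflict arises, but a stopping rule has to work when the treatment is worse than expected.

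**Conclusion.** The concern holds. Two current sections give different boundaries for one safety look, and the more than 2 in Section 4.1 is the wrong number. The contradiction itself needs no assumption. On the count rule, applying the Section 4.1 boundary lowers early stopping at 30% toxicity by 32.4 percentage points and adds about 4.5 patients to expected enrolment (16.42 − 11.88). Those figures assume that the DSMB approves stage 2 whenever the rule allows it. Across assumed Grade 4 shares from 0 to 20%, the loss in early stopping runs from 32.4 down to 20.7 points. The breach of the 10% false-acceptance limit is minor and should not carry the argument. Because this is the trial's only scheduled interim safety rule, it must be corrected before the interim look.

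**What to change.** In Section 4.1, Interim Analysis, change the boundary to termination when more than 1 patient has treatment-related grade ≥3 toxicity. This also restores the treatment-related qualifier, which that paragraph omits but which Section 5.0 and the primary endpoint in Section 4.3 ("the absence of any treatment-related Grade ≥3 adverse events") both use. Leave the boundary, the error rates and the optimal label in Section 5.0 as they are.

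As a minor tidy-up, use one grade 4-or-higher wording in Section 4.1 (General Design and Interim Analysis) and Section 5.0, which now phrase that stop in three ways.

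The cost is one number and a small wording alignment in a protocol amendment. No extra patients, procedures or recalculation are needed.
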